9.3 Retention of Records

Trial-related documents will be maintained by the PI. All trial-related documents will be stored securely to maintain the confidentiality of subjects' personal and health-related information. All records pertaining to this protocol will be stored in a locked cabinet at JHU or at an offsite, locked storage facility per CIR process and regulations.

The FDA requires study records to be retained for up to 2 years after marketing approval or disapproval (21 CFR 312.62), or until at least 2 years have elapsed since the formal discontinuation of clinical development of the investigational agent for a specific indication. These records are also to be maintained in compliance with IRB/Ethics Committee (EC), state, and federal medical records retention requirements, whichever is longest. All stored records are to be kept confidential to the extent provided by federal, state, and local law. It is the investigator's responsibility to retain copies of source documents until receipt of written notification to the contrary from the OCRPRO/DCR/NIAID. No study document should be destroyed without prior written agreement between OCRPRO/DCR/NIAID and the PI. Should the investigator wish to assign the study records to another party and/or move them to another location, the investigator must provide written notification of such intent to OCRPRO/DCR/NIAID with the name of the person who will accept responsibility for the transferred records and/or their new location. NIAID must be notified in writing and written NIAID permission must be received by the site prior to destruction or relocation of research records other than as per CIR SOP.

9.4 Protocol Revisions

No revisions to this protocol will be permitted without documented approval from the Sponsor and the IRB that granted the original approval for the study. This does not apply

to changes made to reduce discomfort or avert risk to study subjects. Furthermore, in the event of a medical emergency, the PI shall perform any medical procedures that are deemed medically appropriate. The PI must notify the Sponsor of all such occurrences.

9.5 Study Monitoring

As per ICH GCP 5.18 and FDA 21 CFR 312.50, clinical protocols are required to be adequately monitored by the study sponsor. This study monitoring will be conducted according to the “NIAID Intramural Clinical Monitoring Guidelines.” Monitors under contract to the OCRPRO/DCR/NIAID will visit the clinical research site to monitor all aspects of the study in accordance with the appropriate regulations and the approved protocol. The objectives of a monitoring visit will be: 1) to verify the existence of signed informed consent documents for each monitored subject; 2) to verify the prompt and accurate recording of all monitored data points and prompt reporting of all SAEs; 3) to compare abstracted information (CRIMSON pulls) with individual subject’s records and source documents (supporting data, laboratory specimen records, clinical notes); and 4) to ensure study subject protection, investigators’ compliance with the protocol, and study record completeness and accuracy. The monitors will also inspect the clinical site regulatory files to ensure that regulatory requirements (Office for Human Research Protections), FDA and applicable guidelines (ICH GCP) are being followed. During the monitoring visits, the PI (and/or designee) and other study personnel will be available to discuss the study progress and monitoring visit.

A specific protocol monitoring plan will be discussed with the PI and study staff prior to enrollment. The plan will outline the frequency of monitoring visits based on such factors as study enrollment, data collection status, and regulatory obligations.

10. STATISTICAL CONSIDERATIONS

10.1 Description of Statistical Methods

This study is exploratory rather than confirmatory; its purpose is to estimate AE rates and patterns of immune responses rather than to test formal statistical hypotheses. Estimates will be presented with their 95% confidence intervals. Sample size was determined based on similar exploratory vaccine trials, and also based on the sizes of the previous cohorts to be recruited into the current study. We would like to enroll at least 12 people who were H2N2, H6N1 and H9N2 pLAIV recipients. In addition, we would like to enroll at least 20 negative controls.

Descriptive approaches will be used to meet the protocol objectives as stated in Section 2 of this protocol, as well as formal statistical tests as outlined below. Results will be presented in tabular format, as well as graphically where appropriate.

10.2 Sample Size Reasoning

The null hypothesis for the study is that the HA stalk antibody response after receipt of the H5N1 pISV in the pLAIV recipients (treatment cohort, T) will be the same as in the naïve (control, C) cohort. The alternative is that the recipients of the pLAIV will have a higher stalk antibody response. Based on the previous studies of H5N1 stalk response in naïve individuals (17, 18), we assume that the naïve cohort will have a 4-fold increase in

antibodies targeting the stalk after the H5N1 pISV. A total of 15 subjects in the pLAIV cohorts will allow for 80% power to detect a 2-fold higher response (8-fold increase in antibody titers), with an alpha of 0.05. 12 subjects in the pLAIV cohort will allow for 80% power to detect a 2.1-fold higher response: an 8.2-fold increase in antibody titers.

10.3 Primary Objective:

To explore the difference in the stalk antibody response against Influenza A group 1 stalks as measured by ELISA and neutralization titer after receipt of the Monovalent Influenza Subvirion Vaccine (H5N1) in previous recipients of H2N2, H6N1 and H9N2 pLAIVs compared with healthy, pLAIV-naïve individuals.

10.4 Primary Endpoint:

1. The fold rise in titer of anti-group 1 stalk-antibodies measured by ELISA and microneutralization assay (MN) using the chimeric cH6/N1 probe, in recipients of the pLAIVs (H2N2, H6N1 and H9N2) compared to the control pLAIV-naïve cohort. In addition to testing sera following administration of the H5N1 subunit vaccine, if possible, this analysis will include sera collected before and after receipt of pLAIV.

Analysis plan: Antibody titers will be converted to a log scale, and comparisons of the antibody titers will be made using a t-test or ANOVA as appropriate.

If more than 2 cohorts are being compared, appropriate post-hoc, pairwise (as applicable) comparisons will be made with appropriate alpha-adjustments if the null hypothesis is rejected.

10.5 Secondary Objective

Assess the reactogenicity of the Monovalent Influenza Subvirion Vaccine (H5N1) in previous recipients of live attenuated influenza vaccine (LAIV) compared with healthy, pLAIV-naïve individuals.

Adverse events will be assessed, graded and recorded for 28 days after vaccination. Serious Adverse Events (SAEs) will be assessed for 3 months after the immunization.

10.6 Secondary Endpoints:

- The number of vaccine-related adverse events in the recipients of the pLAIV compared to the control cohort.

10.7 Exploratory Objectives:

- To assess the biological activity of antibodies to the HA stalk region by passive transfer of serum from study subjects to mice to assess their ability to protect the mice from lethal challenge with an influenza virus
- To correlate ELISA and neutralizing stalk antibody titers with functional ability of the post vaccine serum to protect mice from lethal challenge
- To assess the breadth of the vaccine induced antibody response by using a panel of HAs that include HA stalks from a variety of group 1 and group 2.
- To assess B- cell responses to the pISV in the previous pLAIV recipients compared with naïve individuals.

- To assess the level of serum stalk antibodies after the initial pLAIIV (from stored samples) and compare to the post-pISV response.
- To assess the longevity of the stalk antibody response
- To determine the titer of anti-H5 antibodies in the 2 cohorts of subjects.
- To determine the titer of antibodies directed to the HA received in the pLAIIV doses.

10.8 Exploratory Endpoints:

- Difference in survival rates between mice challenged with H5N1 after passive serum from the subjects previously vaccinated with pLAIIV compared to those receiving serum from the control cohort after vaccination with H5N1 pISV.
- The correlation of the serum stalk antibody titers by neutralization assay and ELISA with the ability of the sera to protect against lethal challenge.
- Measurement of cross-reactivity of antibody responses in pLAIIV primed vs. naïve individuals to a variety of viruses representing multiple HA stalks.
- The percentage of memory B cells against group 1 stalk in the recipients of the pLAIIV compared to the control cohort.
- The level of stalk antibodies generated by the pLAIIV – tested in sera obtained shortly after receipt of pLAIIV and compared to the stalk antibodies generated after receipt of the H5N1 pISV.
- HAI titer against H5 in the pLAIIV primed vs. naïve individuals.
- HAI titer against H2, H6 and H9 in the pLAIIV primed individuals.

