2. OBJECTIVES

2.1 Primary Objective:

To explore the difference in the stalk antibody response against Influenza A group 1 stalks as measured by enzyme-linked immunosorbent assay (ELISA) and neutralization titer after receipt of the Monovalent Influenza Subvirion Vaccine (H5N1) in previous recipients of H2N2, H6N1 and H9N2 pLAIVs compared with healthy, pLAIV-naïve individuals.

2.2 Secondary Objective:

Assess the reactogenicity of the Monovalent Influenza Subvirion Vaccine (H5N1) in previous recipients of live attenuated influenza vaccine (LAIV) compared with healthy, pLAIV-naïve individuals.

Adverse events will be assessed, graded and recorded for 28 days after vaccination. Serious Adverse Events (SAEs) will be assessed for 90 days after the immunization.

2.3 Exploratory Objectives:

- To assess the biological activity of antibodies to the HA stalk region by passive transfer of serum from study subjects to mice to assess their ability to protect the mice from lethal challenge with an influenza virus.
- To correlate ELISA and neutralizing stalk antibody titers with functional ability of the post vaccine serum to protect mice from lethal challenge.
- To assess the breadth of the vaccine induced antibody response.
- To assess plasmablast and memory B cell responses to the pISV in the previous pLAIV recipients compared with naïve individuals.
- To assess the longevity of the stalk antibody response.
- To determine the titer of anti-H5 head antibodies in the 2 cohorts of subjects.
- To determine the titer of antibodies directed to the HA head received in the pLAIV doses.

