8.1.2 Solicited Adverse Events (Protocol-Specified Adverse Events)

AEs will be categorized as Solicited AEs and Other AEs. Solicited AEs are predefined AEs that can potentially occur after vaccine administration. Reactogenicity events are solicited adverse events that occur in the first 7 days after vaccination. The following will be considered solicited AEs for subjects receiving the Monovalent Influenza Subvirion Vaccine (H5N1):

1. Fever $\geq 100.4^{\circ}\text{F}$ (38°C) oral
2. Headache
3. Malaise
4. Nausea
5. Myalgia
6. Injection pain
7. Injection site erythema
8. Injection site swelling
9. Injection site induration
10. Injection site pruritus

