8.2 Recording Period for Adverse Events

- All non-serious AEs will be assessed, recorded and reported for 28 days beginning at study vaccination, and will be followed to resolution, even if more than 28 days, or until the PI deems the event to be chronic or the subject to be stable.
 - Solicited non-serious AEs may be assessed/graded per a different table, if specified herein, and may be recorded and reported separately for tracking purposes.
 - Reactogenicity AEs/events are solicited AEs that are collected in the first 7 days after vaccination and may be recorded and reported separately for tracking purposes.
- SAEs, regardless of causality, will be assessed, recorded and reported for 90 days beginning at study vaccination, and will be followed to resolution, even if more than 90 days, or until the PI deems the event to be chronic or the subject to be stable.
- SUSARs, UPs, and UPnonAEs will be assessed, recorded and reported through the end of the study, beginning at study ENROLLMENT, and will be followed to resolution, even if beyond the end of the study (as may be permissible and possible in consultation with the IRB and sponsor) or until the PI deems the event to be chronic or the subject to be stable.

Assessment of safety will include clinical observation and monitoring of clinical and immunologic parameters. Safety will be evaluated by monitoring of subjects for local and systemic adverse reactions within the first 30 minutes post vaccination. Subjects will return to the clinic on Day 7 following vaccination for in-person clinical assessment.

All AEs will be graded for severity and assessed for relationship to the study product. A study clinician will be available 24 hours a day during the study evaluation period. Should a subject call a study clinician to report an AE, it will be fully documented in the subject's study chart and discussed with the PI. Interim follow-up visits (between protocol scheduled visits) may be scheduled at the PI's discretion if additional assessment is indicated.

All AEs will be captured in the source documents and in Clinical Research Information Management System of the NIAID (CRIMSON). Those assessed as serious will be further reported on the Sponsor's SAE-UP report form. The AEs judged to be possibly, probably, or definitely related to the study product will be followed as specified above, generally until resolution.

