8.3 Association of Adverse Events with Receipt of Study Vaccine

All AEs will have their possible relationship to study vaccine. Causality will be assessed by the PI or designee using the following definition:

Definitely related:	Clear-cut temporal association, and no other possible cause.
Probably related:	Reasonable temporal association and a potential alternative cause is not apparent.
Possibly related:	Less clear temporal association; other causes also possible.
Unlikely related:	Temporal association between the AE and the vaccine or the nature of the event is such that the vaccine is not likely to have had any reasonable association with the observed illness/event (cause and effect relationship improbable but not impossible).
Not Related:	The AE is completely independent of vaccine administration; and/or evidence exists that the event is definitely related to another cause.

The degree of certainty with which an AE can be attributed to administration of the study vaccine will be determined by how well the event can be understood in terms of 1 or more of the following:

1. The event being temporally related with vaccination.
2. A reaction of similar nature having previously been observed with this type of vaccine and/or formulation.
3. The event having often been reported in the literature for similar types of vaccines.

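### The only listed secondary endpoint, a count of vaccine-related adverse events, only partly measures reactogenicity as the protocol defines it

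*Combined protocol and SAP*

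**What the plan says.** At the secondary level, Sections 2.2 and 10.5 share one aim: "Assess the reactogenicity of the Monovalent Influenza Subvirion Vaccine (H5N1) in previous recipients of live attenuated influenza vaccine (LAIV) compared with healthy, pLAIV-naïve individuals".

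The protocol defines the term twice. Section 8.1.2 says "Reactogenicity events are solicited adverse events that occur in the first 7 days after vaccination" and lists ten solicited events. Section 8.2 says "Reactogenicity AEs/events are solicited AEs that are collected in the first 7 days after vaccination" and allows them to be recorded and reported separately. Neither definition mentions causality.

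Section 10.6 lists one secondary endpoint. It begins "The number of vaccine-related adverse events in the recipients of the" and goes on to set prior pLAIV recipients against controls. It names no solicited list, time window, severity grade, relatedness threshold or unit of count.

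Section 8.2 has every adverse event assessed for relationship to the product. In Section 8.3, "Causality will be assessed by the PI or designee using the following definition", on a five-level scale. The title summary and Section 3.1 describe the trial as open-label, and Section 3.5 gives every subject the same single dose of H5N1 pISV.

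The text under the objective in 10.5 adds: "Adverse events will be assessed, graded and recorded for 28 days after vaccination". SAEs are followed for 90 days (2.2) or 3 months (10.5).

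**The concern.** The objective and its endpoint use different rules for which events count. Reactogenicity is fixed by what happened and when. The endpoint is fixed by what an assessor concluded about cause. The plan states this rule outright, so an analyst following 10.6 to the letter would produce a comparison that departs from the stated objective.

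The causality step also brings in a judgement that the reactogenicity definition avoids. Both cohorts receive the same vaccine, so the contrast is prior pLAIV status. An assessor who knows that status could attribute the same symptom differently in the two cohorts. At stake is whether the reported secondary result describes reactogenicity or a mixture of reactogenicity, later events and attribution.

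**Working it through.** The plan gives no rate, power or precision figure for this endpoint, so there is nothing to reproduce. The check is to sort events by the two rules.

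| Event | Reactogenicity (8.1.2, 8.2) | Endpoint (10.6) |
|---|---|---|
| Solicited, first 7 days, judged related | counted | counted |
| Solicited, first 7 days, judged unrelated | counted | omitted |
| Solicited, after Day 7, judged related | not counted | counted |
| Unsolicited, any recorded day, judged related | not counted | counted |

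The rules agree on the first row and differ on the other three. A Day 3 myalgia judged unlikely to be related is a reactogenicity event that the endpoint drops. An unsolicited Day 25 symptom judged possibly related is not a reactogenicity event, but the endpoint counts it. No other secondary or exploratory endpoint in 10.6 or 10.8 covers solicited events.

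**Is the second row likely to hold any events?** Section 8.3 bases attribution on timing, on similar reactions seen before with this type of vaccine, and on the literature. Most solicited events in the first week would probably be called related. However, Section 11.4.3 reports that malaise, myalgia and headache were not statistically more frequent with this vaccine than with placebo. Attribution could therefore reasonably go either way for three of the ten listed events.

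**What could the attribution step do?** Restrict attention to solicited events and let the true rate r be equal in both cohorts. If a1 and a2 are the probabilities that such an event is called related, the endpoint's ratio is (r × a1)/(r × a2) = a1/a2, whatever r is. The documents give no values for a1 or a2. Under assumed pairs:

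- 0.95 and 0.85: 1.12, or 0.89 if reversed
- 0.90 and 0.70: 1.29, or 0.78 if reversed
- 1.00 and 0.60: 1.67, or 0.60 if reversed
- equal probabilities: 1.00

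These ratios restate the assumptions. They show that the endpoint can differ between cohorts with identical reactogenicity, and they say nothing about whether it will.

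**Precision.** Cohort sizes are 12–15 and 20. If half the subjects had an event, the exact (Clopper–Pearson) 95% interval would be 21%–79% for 6/12 and 27%–73% for 10/20. Distortions of the size shown above would be hard to see in the data, so the definition has to be settled in the plan.

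**The case against.** Four arguments limit the point.

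First, a reader might infer that the endpoint fails to measure the objective at all. The documents do not support that. Related solicited events in the first week are counted, and they may be the bulk of reactogenicity. The text under the objective also covers 28-day adverse events and longer SAE follow-up, so a related-event summary is a legitimate safety output there. This stands, and the claim is limited to partial measurement.

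Second, a reader might infer that no other between-cohort safety comparison is planned. Section 10.1 says the study aims to estimate adverse event rates with 95% confidence intervals and will use descriptive methods to meet the Section 2 objectives, and 8.2 permits separate reporting of reactogenicity events. That too stands. What remains is that 10.6 lists only one secondary endpoint, that the wording in 8.2 is permissive, and that no solicited-event table is fixed.

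Third, a reader might infer that attribution will bias the comparison. Nothing shows this. Both cohorts get the same product, no reason or direction for differential attribution is given, and the protocol does not state that the assessor knows the cohort. It is only the case that the trial is open-label and no masking is described.

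Fourth, removing the causality filter does not remove awareness of cohort. Headache, malaise, nausea, myalgia and pain are self-reported, largely graded by function, and still collected open-label. This is correct: the fix removes one subjective step and leaves the others.

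**Conclusion.** The mismatch is real and limited. The listed secondary endpoint captures only part of the stated objective. It omits solicited 7-day events judged unrelated, admits related unsolicited and later events, and depends on an open-label causality judgement. This follows from the text and needs no numerical assumption.

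The effect on the result cannot be sized. It depends on how many events fall in the discordant categories and on how attribution is applied, and the documents give neither. The ratios above are not estimates of bias.

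The study is exploratory, the endpoint is secondary, and the primary immunogenicity comparison is untouched. It is still worth correcting, because estimating adverse event rates is a declared purpose and the correction is small.

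**What to change.** Add to Section 10.6, as the endpoint that matches the objective: the number and proportion of subjects per cohort with each solicited adverse event listed in 8.1.2 with onset in the first 7 days, by maximum grade, regardless of attributed causality, with exact 95% confidence intervals.

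Keep vaccine-related adverse events to Day 28 and SAEs to Day 90 as separate safety outputs. For the related events, state the relatedness threshold and whether events or subjects are counted.

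Three details need settling in the text:

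- **Window.** Define it by onset and name the study days it covers. Section 8.1.2 speaks of events occurring in the window, and 8.2 of events collected in it.
- **Onset day.** The sponsor should confirm that it is recorded, since the documents do not name that field and describe no diary. The Day 7 visit has a margin of ±1 day, so for a subject seen on Day 6 the end of the window depends on what is captured later.
- **Grading scale.** Section 8.4 sends solicited events to Appendix B but also applies Table 2 to all adverse events. Name Appendix B for this endpoint, with Table 3 of Section 8.4 for fever, which Appendix B does not grade.

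The cost is one more table and a short edit. Solicited events are already collected and graded, so no new visit or procedure appears necessary, provided onset day is captured.

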11. HUMAN SUBJECT PROTECTIONS AND ETHICAL OBLIGATIONS

This research will be conducted in compliance with the protocol, GCP, and all applicable regulatory requirements.

